Amendment rationale

This protocol amendment is issued for the following reasons:

- Based on results from MEASURE III (CAIN457F2314), MEASURE IV (CAIN457F2320) and COAST V (Ixekizumab NCT02696785) studies, the assumptions for the power calculation of the primary and a selection of secondary and exploratory objectives were reevaluated, leading to changes in the statistical analysis plan. The three studies mentioned above suggest that the placebo response might be somewhat higher, leading to a potentially smaller difference between active treatment and placebo than assumed during the planning of this trial. Therefore, in order to keep sufficient power, it was decided to pool the two Secukinumab arms for the primary analysis. This new evaluation triggered an adaption of a set of objectives. The primary objective was adapted so that data of *Group 1* (Secukinumab 150 mg s.c. "delayed tapering") and of *Group 2* (Secukinumab 150 mg s.c. "early tapering") are pooled and ASAS20 response at week 12 are compared against placebo. For the other reevaluated secondary and exploratory objectives, data is pooled and is compared against placebo according to the same schema. In the course of this amendment the amount of randomized patients can be reduced to a smaller size (approx. 190) than originally expected (approx. 204), while maintaining adequate power for primary and secondary analyses.
- The amendment is used to describe the ASAS Health Index (chapter 6.4.9) in a more detailed way. Besides the 17 aspects of health, the 9 questions regarding environmental factors in patients with AS are mentioned.

None of the changes described in this amended protocol are made due to newly emerged safety considerations.

1 Introduction

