H₁₀: Secukinumab 150 mg s.c. (early tapering) is not different to placebo regimen with respect to change from baseline in total BASDAI score at Week 12

H₁₁: Secukinumab 150 mg s.c. (early tapering) is not different to placebo regimen with respect to change from baseline in total BASDAI score at Week 16

These hypotheses will in principal be tested hierarchically in ascending order. However, since some hypotheses for individual group comparisons are already contained in the higher-ranked, pooled comparisons for the same endpoint (i.e. H4 and H5 are contained in H1, H7 and H8 are contained in H₂ and H₁₀ are contained in H₃) these individual hypothesis can be tested simultaneously. The justification is that as soon as the pooled hypothesis has been rejected (e.g. H₁), at least one of the two contained individual hypotheses (e.g. H₄ and H₅) must be false and there is only a potential for at most one type-I-error. Therefore H₄ and H₅ can be tested simultaneously once all higher-ranked hypotheses have been rejected. The same argument applies to H₇ and H₈ and to H₉ and H₁₀. The following chart displays the testing strategy graphically:

First the hypotheses (H_1) for the primary objective (ASAS20 for Secukinumab pooled at week 12) versus placebo will be tested. If this hypothesis can be rejected at level α , H_2 will be tested and so on until H_4 . H_4 . and H_5 will be tested simultaneously. If both can be rejected, H_6 will be tested and so on. As soon as a hypothesis fails to be rejected at level α , all tests of the following hypotheses (except the paired hypothesis in the same knot) will be regarded as exploratory only and will not provide any confirmatory evidence, irrespective of their nominal p-values. Of note, in the description above, rejection of a hypothesis refers to rejection of the two-sided hypothesis; however the level of a rejected hypothesis is only passed on according

to the procedure for the test of another hypothesis if the treatment effect is in favor of the Secukinumab regimen. The family-wise error will be set to $\alpha=5\%$ and it will be controlled with the proposed semi-hierarchical testing strategy.

ASAS20 at week 12

Response at Week 12 to ASAS20 for Secukinumab (delayed-tapering) versus placebo will be evaluated using a logistic regression model with treatment as a factor and baseline weight as a covariate.

ASAS20 at week 16

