9.7 Sample size calculation

All sample size and power considerations are performed using EAST 6.

The sample size was calculated based on the phase III results of the MEASURE2 study, which used the same dose and loading regimen as will be applied in this trial. Under the assumption of 56.9% ASAS20 responders in the Secukinumab (delayed tapering) group and 27.0% in the placebo group, a sample size of 62 patients per group is required to have 90% power to show superiority of Secukinumab over placebo at a two sided $\alpha=5\%$.

For the comparison of the the early tapering group at week 16 vs. placebo, the same treatment effect is expected, leading to the same sample size. To compensate for some dropout and other protocol deviations, the sample size will be increased to 68 per arm. The total sample size of this trial will thus be 204. At the time of writing this amendment, about 190 patients have been recruited into this trial and it seems unlikely that a sample > 200 can be recruited within reasonable time. With this sample size, the (newly introduced) comparison of pooled

Secukinumab groups vs. placebo, the trial would still have almost 80 % (78%) power if the placebo response was somewhat higher (35%) than originally assumed...

Other secondary endpoints

It will be assumed that the amount of NSAID reduction observed in the etanercept SPARSE trial (Dougados et al. 2014), of 63.9 vs. baseline (etanercept) and 36.6 for placebo, with an estimated standard deviation of 40 will be seen in this trial for both Secukinumab groups versus placebo. Based on this assumption both secukinmab groups will have >90% power to show superiority over placebo for NSAID reduction.

For the total BASDAI parameter, 62 patients per treatment group should yield a power of approximately 91%, assuming a a treatment difference of 1.8 with a standard deviation of 2.8 (van der Heijde 2006). For SF-36 PCS, 62 patients per treatment group yield a power of approximately 87.5%, assuming mean change of 6.9 on both Secukinumab regimen and mean change of 1.6 on placebo with common standard deviation of 8.7 (Davis 2007).

10 Ethical considerations

Study documentation, record keeping and retention of documents

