## 2 Statistical methods

### 2.1 Data analysis general information

The data will be analyzed by Novartis on all patient data after database lock for the respective trial period. It is planned that the data from all centers that participate in this protocol will be used for analysis. Analysis datasets and statistical outputs will be produced using the most recent SAS® Version 9.4 (SAS Institute Inc., Cary, NC, USA), and stored in Novartis global programming & statistical environment (GPS).

Continuous data will be summarized by n, mean, standard deviation (SD), median, first and third quartiles, minimum and maximum. Categorical data will be presented by absolute and relative frequencies (n and %). Summary statistics will also be presented graphically wherever applicable.

If not otherwise specified, p-values and confidence intervals will be two-sided. Unless otherwise stated, the level of significance will be set to 5% (two-sided, family-wise type-I-error).

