## 3 Sample size calculation

All sample size and power considerations are performed using EAST 6.

The sample size was calculated based on the phase III results of the MEASURE2 study, which used the same dose and loading regimen as will be applied in this trial. Under the assumption of 56.9% ASAS20 responders in the Secukinumab (delayed tapering) group and 27.0% in the placebo group, a sample size of 62 patients per group is required to have 90% power to show superiority of Secukinumab over placebo at a two sided  $\alpha=5\%$ .

For the comparison of the the early tapering group at week 16 vs. placebo, the same treatment effect is expected, leading to the same sample size. To compensate for some dropout and other protocol deviations, the sample size will be increased to 68 per arm. The total sample size of this trial will thus be 204. At the time of writing the amendment, about 190 patients have been recruited into this trial and it seems unlikely that a sample  $> 200$  can be recruited within reasonable time. With this sample size, the (newly introduced 190) comparison of pooled Secukinumab groups vs. placebo, the trial would still have almost 80 % (78%) power if the placebo response was somewhat higher (35%) than originally assumed.

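### The amendment claims adequate power for the secondary analyses, but at its own 35% placebo scenario the single-arm ASAS20 tests have about 63–70% power, and the >90% for each arm's NSAID reduction ignores the gates in front of it

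*Protocol*

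**What the plan says.** **Original sizing (Protocol 9.7, repeated in SAP 3).** The rates are set out thus: "Under the assumption of 56.9% ASAS20 responders in the Secukinumab (delayed tapering) group and 27.0% in the placebo group". From them the plan derives 62 per arm for 90% power, testing at two-sided 5%. For the other arm: "For the comparison of the the early tapering group at week 16 vs. placebo, the same treatment effect is expected". The 62 per group was raised to 68 for dropout and protocol deviations.

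**Amendment.** The Amendment rationale reports that newer studies suggest a higher placebo response, pools the two secukinumab arms for the primary test, and reduces the size from about 204 to about 190, "while maintaining adequate power for primary and secondary analyses". The supporting recalculation covers one test, the pooled one: "the trial would still have almost 80 % (78%) power if the placebo response was somewhat higher (35%) than originally assumed".

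**NSAID reduction (Protocol 9.7).** Reductions of 63.9 and 36.6 are assumed, with SD 40. "Based on this assumption both secukinmab groups will have >90% power to show superiority over placebo for NSAID reduction".

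**Testing order (Protocol 9.5.1, SAP 2.7.2).** H1 (ASAS20), H2 (ASAS-NSAID) and H3 (BASDAI) are pooled tests at Week 12. H4 (delayed arm) and H5 (early arm) are the single-arm ASAS20 tests at Week 12, tested together. H6 is the early arm's ASAS20 at Week 16. H7 and H8 are the single-arm NSAID tests. H6 is reached only if both H4 and H5 are rejected, and H7 and H8 only after H6. After a failure, all later tests ("except the paired hypothesis in the same knot) will be regarded as exploratory only and will not provide any confirmatory evidence". The family-wise level is 5% two-sided.

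Neither document gives single-arm ASAS20 power at 35% placebo, power within the hierarchy, or an assumed early-arm response at Week 12.

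**The concern.** The amendment was prompted by the prospect of a higher placebo response, and it reassures the reader about both primary and secondary analyses. Only H1 was reworked for that prospect. The 90% for a single arm was computed at 27% placebo and does not carry over to 35%.

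The NSAID figure has a second gap. It is the power of one test taken alone, while the plan lets H7 and H8 count only after six other hypotheses have been rejected, three of them single-arm ASAS20 tests. The study is meant to inform when NSAIDs can be tapered, so the per-regimen NSAID claims matter. A reader who takes >90% as the chance of a confirmatory claim for each regimen is misled.

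H5 adds an unstated assumption. The early arm starts secukinumab at Week 4, so Week 12 is after 8 weeks of drug. The plan assumes the full effect in that arm only at Week 16, yet H1 and H5 use Week 12, and H5 stands in front of H6.

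**Working it through.** **Inputs.** From Protocol 9.7: ASAS20 56.9% active, 27.0% or 35% placebo; NSAID difference 63.9 − 36.6 = 27.3, SD 40; BASDAI difference 1.8, SD 2.8; about 190 patients. Allocation is 1:1:1 (Protocol 3.1), hence about 63 per arm. Two-sided 5%.

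**Formula for two proportions.** Power = Φ[(p1 − p0 − c − 1.96·s0)/s1], where s0 = √[p̄(1 − p̄)(1/n0 + 1/n1)], s1 = √[p0(1 − p0)/n0 + p1(1 − p1)/n1], p̄ is the average response weighted by group size, and c = ½(1/n0 + 1/n1) with continuity correction or 0 without.

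**1. Reproduce the plan's figures.**
- 56.9% vs 27%, 62 per group: (0.299 − 0.0161 − 1.96 × 0.0886)/0.0845 = 1.29, power 90.2%. This matches the stated 62 for 90%. Without correction it is 93.1%.
- 56.9% vs 35%, 127 pooled vs 63: (0.219 − 0.0119 − 1.96 × 0.0770)/0.0744 = 0.75, power about 77.5%; with 128 vs 64 it is 78.1%. This matches the stated 78%. Without correction it is 81.9% (127 vs 63).

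So the plan used the continuity correction. The 78% also implies 56.9% for the pooled arms at Week 12, and hence, if the delayed arm is at 56.9%, the full effect in the early arm after 8 weeks.

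**2. Single-arm ASAS20, 63 vs 63.**
- 35% placebo, corrected: (0.219 − 0.0159 − 1.96 × 0.0888)/0.0866 = 0.336, power 63.2%. Fisher's exact test gives 66.5%. Uncorrected: (0.219 − 0.1740)/0.0866 = 0.519, power 69.8%.
- 27% placebo, corrected: (0.299 − 0.0159 − 1.96 × 0.0879)/0.0838 = 1.32, power 90.7%. The original 90% therefore survives the smaller size at 27%, with no allowance for dropout.

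**3. NSAID reduction, one arm alone.** SE = 40 × √(2/62) = 7.18; 27.3/7.18 = 3.80; Φ(3.80 − 1.96) = 96.7%. The stated >90% is correct as a single-test figure.

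**4. Upper bound in the hierarchy.** H7 and H8 need H4, H5 and H6 to be rejected first. Whatever the correlations, their confirmatory power cannot exceed that of any one of those tests: about 63–70% at 35% placebo.

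**5. Simulation of the order H1 to H8.** 63 per arm, 60,000 trials per setting, 56.9% in both active arms at both visits, 35% placebo at both visits, two-sample tests without covariates. Assumed because the plan does not give them: latent Week 12/16 ASAS20 correlation 0 to 0.9, and correlation of ASAS20 with the NSAID and BASDAI outcomes 0 to 0.4.

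| Rejected (35% placebo) | Corrected | Uncorrected |
|---|---|---|
| H1 | 77–78% | 81–82% |
| H1–H3 | 76–77% | 79–81% |
| H4 (or H5) within the hierarchy | 62–63% | 68–69% |
| H4 and H5 both, ignoring H1–H3 | 51% | 58–59% |
| H7 (or H8) within the hierarchy | 32–43% | 40–50% |

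Working with test statistics instead of patients gives 37–51% uncorrected for H7 or H8, so the overall range is about 32–51%. Simulated single-arm ASAS20 power is a little above the formula (66–67% corrected, 72–73% uncorrected), so the table does not understate the plan's position. At 27% placebo the same simulation gives H7 or H8 about 75–79% corrected and 80–84% uncorrected.

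**The case against.** **The NSAID figure contains no arithmetic error.** This stands. Section 9.7 never calls its >90% a probability within the hierarchy. The fault is that it is unlabelled beside a testing order that decides whether the result counts.

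**35% is a what-if.** This also stands. A reader might infer that the amendment replaced 27% by 35%; the text keeps 27.0% as the sizing basis and offers 35% as a possibility. It is still the only scenario the amendment evaluates, and the reason given for pooling, so the adequacy claim should be tested there. Even at 27% the gated NSAID power is about 75–84%.

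**Not every secondary or NSAID test is weak.** A reader might infer that all are. The pooled NSAID test H2 is gated only by H1, and H3 only by H1 and H2; both keep about 76–81% at 35%. H4 and H5 each remain confirmatory if the other fails.

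**The gated figure is not fixed by the documents.** Correct: it needs correlations they do not supply, so a single value or narrow band would be unsupported. The bound in step 4 needs none.

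**The early-arm rate at 8 weeks is unknown.** One could insert a lower rate and show larger losses, but the documents give no such rate for this regimen. They report superiority as early as Week 1 in one trial and a 59% response at Week 6 in another with intravenous dosing. What can be said is that the assumption is missing.

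**Recruitment was nearly complete.** True: about 190 patients were already in. This point changes neither the design nor the error control, only what the documents claim.

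**Conclusion.** The adequate-power statement is not supported for the single-arm tests in the scenario that prompted the amendment. At 35% placebo and 63 per arm, H4 and H6 have about 63% power by the plan's own method (66% Fisher, 70% uncorrected). So does H5, if the early arm has already reached 56.9% at Week 12. Rejecting both H4 and H5 has about 51–59%. Confirmatory power for H7 or H8 is at most about 63–70% and roughly 32–51%, against a stated >90% that holds only for the test in isolation.

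This rests on 56.9% in both active arms, no loss from 190 patients and no covariate adjustment; the gated range also rests on the assumed correlations. Dropouts count as non-responders, so dropout or a smaller early-arm effect at Week 12 would lower the figures. The single-arm figures and the bound are firm under these inputs; the exact gated value is not. The documents do not support reading the >90% as miscalculated, or the pooled tests H1–H3 as seriously short of power.

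**What to change.** In Protocol 9.7 and SAP 3:

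- Restate power at about 63 per arm for both 27% and 35% placebo: single-test power for H4–H6, and within-hierarchy power for H2–H8, as ranges with the correlation assumptions and test convention stated.
- Label the >90% for NSAID reduction as the power of a stand-alone test.
- State the early-arm ASAS20 response at Week 12 assumed for H1 and H5.

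In the Amendment rationale, limit the adequate-power sentence to the pooled tests H1–H3.

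The cost is wording and one simulation. The stated figures become less favourable; no extra patients and no change to the tests are needed.

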10.1 Regulatory and ethical compliance

This clinical study was designed and shall be implemented and reported in accordance with the ICH Harmonized Tripartite Guidelines for Good Clinical Practice, with applicable local regulations (including European Directive 2001/20/EC, US CFR 21, and Japanese Ministry of Health, Labor, and Welfare), and with the ethical principles laid down in the Declaration of Helsinki.

10.2 Informed consent procedures

Eligible patients may only be included in the study after providing written (witnessed, where required by law or regulation), IRB/IEC-approved informed consent. Informed consent must be obtained before conducting any study-specific procedures (i.e. all of the procedures described in the protocol). The process of obtaining informed consent should be documented in the patient source documents.

Novartis will provide to investigators in a separate document an informed consent form that complies with the ICH GCP guideline and regulatory requirements and is considered appropriate for this study.

Women of child bearing potential should be informed that taking the study treatment may involve unknown risks to the fetus if pregnancy were to occur during the study and agree that in order to participate in the study they must adhere to the contraception requirement for the duration of the study or longer if required by locally approved prescribing information (e.g. 20 weeks in EU). If there is any question that the patient will not reliably comply, they should not be entered in the study.

10.3 Responsibilities of the investigator and IRB/IEC

Before initiating a trial, the investigator/institution should obtain approval/favorable opinion from the Institutional Review Board/Independent Ethics Committee (IRB/IEC) for the trial protocol, written informed consent form, consent form updates, patient recruitment procedures (e.g., advertisements) and any other written information to be provided to patients. Prior to study start, the investigator is required to sign a protocol signature page confirming his/her agreement to conduct the study in accordance with these documents and all of the instructions and procedures found in this protocol and to give access to all relevant data and records to Novartis monitors, auditors, Novartis Quality Assurance representatives, designated agents of Novartis, IRBs/IECs, and regulatory authorities as required. If an inspection of the clinical site is requested by a regulatory authority, the investigator must inform Novartis immediately that this request has been made.

10.4 Publication of study protocol and results

Novartis assures that the key design elements of this protocol will be posted in a publicly accessible database such as clinicaltrials.gov. In addition, upon study completion and finalization of the study report the results of this trial will be either submitted for publication and/or posted in a publicly accessible database of clinical trial results.

11 Protocol adherence

This protocol defines the study objectives, the study procedures and the data to be collected on study participants. Additional assessments required to ensure safety of patients should be administered as deemed necessary on a case by case basis. Under no circumstances should an investigator collect additional data or conduct any additional procedures for any research related purpose involving any investigational drugs.

Investigators ascertain they will apply due diligence to avoid protocol deviations. If an investigator feels a protocol deviation would improve the conduct of the study this must be considered a protocol amendment, and unless such an amendment is agreed upon by Novartis and approved by the IRB/IEC and health authorities, where required, it cannot be implemented. All significant protocol deviations will be recorded and reported in the CSR.

11.1 **Protocol Amendments**

Any change or addition to the protocol can only be made in a written protocol amendment that must be approved by Novartis, Health Authorities where required, and the IRB/IEC prior to implementation. Only amendments that are intended for patients safety may be implemented immediately provided the Health Authorities are subsequently notified by protocol amendment and the reviewing IRB/IEC is notified. Notwithstanding the need for approval of formal protocol amendments, the investigator is expected to take any immediate action required for the safety of any patient included in this study, even if this action represents a deviation from the protocol. In such cases, the reporting requirements identified in section 7 Safety Monitoring should be followed.

12 References

References are available upon request

13.1 Appendix 1: Clinically notable laboratory values and vital signs

The following criteria will be used to define expanded limits and notable abnormalities of key laboratory tests.

Clinically notable values will be forwarded to Novartis/CRO at the same time that they are sent to investigators. Any action based on these laboratory values should be discussed with Novartis/CRO personnel.

Table 13-1 Safety analyses: expanded limits and notable criteria

Amended Protocol Version v01 Clean

		Notable Criteria							
Laboratory Variable		Standard Units	SI Units						
LIVER FUNCTION AND RELATED VARIABLES									
SGOT (AST)		>3 x ULN	>3 x ULN						
SGPT (ALT)		>3 x ULN	>3 x ULN						
Bilirubin		>2 x ULN	>2 x ULN						
Alkaline phosphatase		>2.5 x ULN	>2.5 x ULN						
RENAL FUNCTION, METABOLIC AND ELECTROLYTE VARIABLES									
Creatinine (serum)		>2 x ULN	>2 x ULN						

HEMATOLOGY VARIABLES

Hemoglobin:

20 g/L decrease from baseline

Platelet count:

<100x10E9/L

White blood cell count:

< 0.8 x LLN

Neutrophils:

<0.9 x LLN

Appendix 2: Liver event and laboratory trigger definitions and 13.2 follow-up requirements

Liver event and laboratory trigger definitions **Table 13-2**

	Definition/ threshold
LIVER LABORATORY	3 x ULN < ALT / AST \leq 5 x ULN
TRIGGERS	$1.5 \times ULN < TBL \le 2 \times ULN$
LIVER EVENTS	ALT or AST > 5 × ULN
	ALP > 2 × ULN (in the absence of known bone pathology)
	TBL > 2 × ULN (in the absence of known Gilbert syndrome)
	ALT or AST > 3 × ULN and INR > 1.5
	Potential Hy's Law cases (defined as ALT or AST > 3 × ULN and TBL > 2 × ULN [mainly conjugated fraction] without notable increase in ALP to > 2 × ULN)
	Any clinical event of jaundice (or equivalent term)
	ALT or AST > 3 × ULN accompanied by (general) malaise, fatigue, abdominal pain, nausea, or vomiting, or rash with eosinophilia Any adverse event potentially indicative of a liver toxicity *
	Any adverse event potentially indicative of a liver toxicity

Table 13-3 Follow-up requirements for liver events and laboratory triggers

Criteria	Actions required	Follow-up monitoring
Potential Hy's Law case ^a	Discontinue the study drug immediately Hospitalize, if clinically appropriate Establish causality Complete liver CRF	ALT, AST, TBL, Alb, PT/INR, ALP and γGT until resolution ^c (frequency at investigator discretion)

Criteria	Actions required	Follow up monitoring
ALT or AST	Actions required	Follow-up monitoring
> 8 × ULN	Discontinue the study drug immediately Hospitalize if clinically appropriate Establish causality Complete liver CRF	ALT, AST, TBL, Alb, PT/INR, ALP and γGT until resolution ^c (frequency at investigator discretion)
> 3 × ULN and INR > 1.5	Discontinue the study drug immediately Hospitalize, if clinically appropriate Establish causality Complete liver CRF	ALT, AST, TBL, Alb, PT/INR, ALP and γGT until resolution ^c (frequency at investigator discretion)
> 5 to ≤ 8 × ULN	Repeat LFT within 48 hours If elevation persists, continue follow-up monitoring If elevation persists for more than 2 weeks , discontinue the study drug Establish causality Complete liver CRF	ALT, AST, TBL, Alb, PT/INR, ALP and γGT until resolution ^c (frequency at investigator discretion)
> 3 × ULN accompanied by symptoms ^b	Discontinue the study drug immediately Hospitalize if clinically appropriate Establish causality Complete liver CRF	ALT, AST, TBL, Alb, PT/INR, ALP and γGT until resolution ^c (frequency at investigator discretion)
> 3 to ≤ 5 × ULN (patient is asymptomatic) ALP (isolated)	Repeat LFT within the next week If elevation is confirmed, initiate close observation of the patient	Investigator discretion Monitor LFT within 1 to 4 weeks
> 2 × ULN (in the absence of known bone pathology)	Repeat LFT within 48 hours If elevation persists, establish causality Complete liver CRF	Investigator discretion Monitor LFT within 1 to 4 weeks or at next visit
TBL (isolated) > 2 × ULN (in the absence of known Gilbert syndrome)	Repeat LFT within 48 hours If elevation persists, discontinue the study drug immediately Hospitalize if clinically appropriate Establish causality Complete liver CRF	ALT, AST, TBL, Alb, PT/INR, ALP and yGT until resolution ^c (frequency at investigator discretion) Test for hemolysis (e.g., reticulocytes, haptoglobin, unconjugated [indirect] bilirubin)
> 1.5 to ≤ 2 × ULN (patient is asymptomatic)	Repeat LFT within the next week If elevation is confirmed, initiate close observation of the patient	Investigator discretion Monitor LFT within 1 to 4 weeks or at next visit
Jaundice	Discontinue the study drug immediately Hospitalize the patient Establish causality Complete liver CRF	ALT, AST, TBL, Alb, PT/INR, ALP and γGT until resolution ^c (frequency at investigator discretion)

Criteria	Actions required	Follow-up monitoring
Any AE potentially indicative of a liver toxicity*	Consider study drug interruption or discontinuation Hospitalization if clinically appropriate Establish causality Complete liver CRF	Investigator discretion

^{*}These events cover the following: hepatic failure, fibrosis and cirrhosis, and other liver damage-related conditions; the non-infectious hepatitis; the benign, malignant and unspecified liver neoplasms

^b(General) malaise, fatigue, abdominal pain, nausea, or vomiting, or rash with eosinophilia ^cResolution is defined as an outcome of one of the following: (1) return to baseline values, (2) stable values at three subsequent monitoring visits at least 2 weeks apart, (3) remain at elevated level after a maximum of 6 months, (4) liver transplantation, and (5) death.

